## **STOP SHOCK LVAD study**

05/29/2019

Pg 4

**Data for Supplemental Protocol Document**  
**Ultra-conservative Programming by Vendor**

Manufacturer	Monitor Zone	VT Zone Detection	VT Zone Therapy	VF Zone Detection	VF Zone Therapy
Abbott	Rate: 150 bpm	Off	Off	Rate: 250 bpm 100 intervals (25s) to detection	ATP x1 (prior to charge) 36J, 40J x5
Biotronik	Rate: 150 bpm	Off	Off	Rate: 250 bpm 30/40 intervals (10 s) to detection	ATP x 1 (prior to charge) ***J
Boston Scientific	Rate: 150 bpm	Off	Off	Rate: 250 bpm 15s to detection	ATP x1 (quick convert) 41J x8
Medtronic	Rate: 150 bpm	Off	Off	Rate: 250 bpm 120/160 intervals (40s) to detection	ATP x1 (prior to charge) 35J x6

*Proposed care pathway ICD re-programming if a) asymptomatic shock in standard programming arm; or b) symptoms prompting external cardioversion in ultra-conservative programming arm*

Manufacturer	Monitor Zone	VT Zone Detection	VT Zone Therapy	VF Zone Detection	VF Zone Therapy
Abbott	Rate: 150 bpm	Rate: 10 bpm below clinical VT 100 intervals to detection	ATP x 30 (20-pulse burst)	Rate: 250 bpm 100 intervals (25s) to detection	ATP x1 (prior to charge) 36J, 40J x5
Biotronik	Rate: 150 bpm	Rate: 10 bpm below clinical VT 32 intervals to detection	ATP x 20 (10-pulse burst)	Rate: 250 bpm 30/40 intervals (10 s) to detection	ATP x 1 (prior to charge) 40J x6
Boston Scientific	Rate: 150 bpm	Rate: 10 bpm below clinical VT 30s to detection	ATP x 60 (30-pulse burst)	Rate: 250 bpm 15s to detection	ATP x1 (quick convert) 41J x8
Medtronic	Rate: 150 bpm	Rate: 10 bpm below clinical VT 130 intervals to detection	ATP x 10 (15-pulse burst)	Rate: 250 bpm 120/160 intervals (40s) to detection	ATP x1 (prior to charge) 35J x6

**Follow Up**

	Screening Enrollment	1 mo	3 mo	6 mo	9 mo	12 mo	15 mo	18 mo	21 mo	24 mo
History, demographics, cardiac test results	x									
Informed Consent	x									
Randomization	x									
Office Visit	x		x	x		x		x		x
Research Visit *, including assessment for AE/SAE/QOL		x			x		x		x	
Device interrogation/data (may be remote)		x	x	x	x	x	x	x	x	x

*\*Can be completed in-office, by phone, medical record review and from the Interagency Registry of Mechanically Assisted Circulatory Support/NIH registry.*

*All visits follow the schedule of routine LVAD follow up.*

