**-Standardized ultra-conservative Or Physician-directed ICD programming for SHOCK reduction among patients on continuous flow LVAD support: a randomized controlled trial (STOP SHOCK LVAD study)**

Study Design	Randomized unblinded clinical trial
Planned Number of Patients	280 patients; 140 per treatment arm
Randomization Method	REDCap
Treatment Arms	A) Ultraconservative ICD programming for maximal shock avoidance (see table at end of protocol)  B) Physician Discretion
Primary Endpoints	Any ICD shock Mortality Syncope
Secondary Endpoints	Time to first ICD shock Time to first ICD shock for VT/VF Quality of Life questionnaire Hospitalizations; including HF and ventricular arrhythmia
Inclusion Criteria	
 
- >18 years of age
 
- Pre-existing ICD
 

Exclusion Criteria	
 
- Non-functional ICD system
 
- Uncontrolled ventricular arrhythmias <math>\leq 7</math> days of enrollment (defined as VT/VF >30 seconds and/or causing hemodynamic instability and/or symptoms or pre-syncope or syncope)
 

Follow-up schedule	Routine post-LVAD care; no additional study visits  Remote ICD monitoring encouraged
Study Duration	2 years

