## **INTRODUCTION**

The proposed study will evaluate the utilization of an ultra-conservative programming strategy to reduce shocks for ventricular arrhythmias (VA) in heart failure (HF) patients with an implantable cardioverter-defibrillator (ICD) and a continuous-flow (CF) left ventricular assist device (LVAD). The survival benefit of ICDs with VA detections and therapies enabled has been established in HF patients with reduced ejection fraction (EF) without LVAD, as well as HF patients with older-generation, pulsatile-flow (PF) LVADs. However, newer studies do not demonstrate the same benefit of VA tachy-therapy in patients with current-generation CF LVAD devices, potentially due to better hemodynamic tolerability of VA. In addition, ICD shocks are known to worsen clinical outcomes while causing patients psychosocial harm. Recent studies have applied extended-detection programming to successfully reduce ICD shocks in non-LVAD HF patients. However, shock reduction strategies have not been previously evaluated in LVAD patients in an adequately-powered, randomized clinical trial. This study will prospectively randomize HF patients with pre-existing ICDs to programming at the discretion of their EP provider versus “ultra-conservative” ICD programming, in which a single ventricular fibrillation (VF) zone will be programmed using the maximum rate cutoff allowable across all ICD manufacturers (250 beats per minute [bpm]), as well as the manufacturer-specific maximum detection intervals. In the ultra-conservative arm, a monitor-only zone will be programmed at 150 bpm. The primary endpoint will be the percentage of patients receiving an ICD shock at 2-year follow-up with planned interim analyses at 6 months and 1 year. Secondary endpoints include time to first ICD shock, time to first VT/VF shock, and Quality Life questionnaires. Data collected will include mortality, syncope, LVAD-related hospitalizations (including HF, VA), and the percentage of patients receiving inappropriate ICD shocks at 2-year follow-up. The study hypothesis is that the standardized application of ultra-conservative ICD programming will reduce shocks and improve quality of life without an increase in mortality, syncope, or hospitalizations compared to physician discretion programming in CF LVAD patients.

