## **OBJECTIVES AND ENDPOINTS**

To evaluate the utilization of an “ultra-conservative,” single-zone programming strategy for ICD tachy-therapies in CF LVAD patients as compared to a passive strategy of standard programming (at the discretion of the provider). The study hypothesis is that an ultra-conservative strategy will result in a reduction in shocks and an improvement in quality of life without increasing adverse outcomes including death, hospitalization, and syncope among patients on CF LVAD support.

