### *Statistical Plan*

At the end of study enrollment, baseline characteristics will be compared with potential covariates of interest able to later be balanced either via multi-variable regression or propensity analysis if needed. For continuous outcomes, linear regression will be utilized, for categorical outcomes, logistic regression will be utilized, and for time to event outcomes, Cox regression will be utilized.

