### *Study Population*

Patients will be eligible for study enrollment and randomization if adult (>18 years old) with a pre-existing, active ICD prior to CF LVAD implantation. Possible study enrollment will be discussed with eligible patients by their treating medical teams and the dedicated study research coordinator during

their index LVAD hospitalization. Consent and randomization will occur either at the time of index hospitalization discharge or during the first post-discharge LVAD/ICD clinic visit, whichever comes first.

*Inclusion:*

- >18 years of age
- Pre-existing ICD

*Exclusion:*

- Non-functional ICD system
- Uncontrolled ventricular arrhythmias  $\leq 7$  days of enrollment (defined as VT/VF  $>30$  seconds and/or causing hemodynamic instability and/or symptoms or pre-syncope or syncope)

Of note, the need for anti-arrhythmic (AAT) drug therapy and/or catheter ablation is not an exclusion criteria, with treatment of VA per treatment team discretion and non-protocol driven. Ventricular ectopy and/or palpitations associated with non-sustained VT also do not serve as an exclusion criteria.

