## **Randomization**

Randomization to ultra-conservative versus standard programming will occur at the time of study enrollment using REDCap. Randomization will be a 1:1 ratio. Neither the patient nor treatment team are blinded to the randomization or programming assignment. ICD re-programming will occur in the device clinic or patient hospital room as per the current routine care pathway.

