## **ICD Programming**

There will be no study-related diagnostic tests, treatments, or follow-up visits beyond routine post LVAD care. The ICD re-programming will be performed during the routine pre-discharge ICD check during the LVAD implant hospitalization or at routine LVAD clinic follow-up  $\leq 30$  days. For patients experiencing sustained VA below the VT zone in the ultra-conservative pathway, a symptom-driven care pathway will be implemented involving same-day cardioversion with the associated routine care. In the physician-discretion arm, ICD shocks delivered for VA routinely result in emergency department visits and hospitalizations, which fall under usual care covered by private and public payers.

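### No quality-of-life score is scheduled before the unblinded randomisation; collecting one at enrolment and adjusting for it would cheaply sharpen a secondary endpoint that is part of the hypothesis

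*Combined protocol and SAP*

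**What the plan says.** The synopsis lists "Quality of Life questionnaire" among the secondary endpoints. The Introduction expects the ultra-conservative strategy to reduce shocks and "improve quality of life without an increase in mortality, syncope, or hospitalizations compared to physician discretion programming in CF LVAD patients". Objectives and Endpoints repeats that the strategy "will result in a reduction in shocks and an improvement in quality of life".

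In the Follow Up table one row names QOL: "Research Visit *, including assessment for AE/SAE/QOL". It is marked at 1, 9, 15 and 21 months. The rows marked at Screening/Enrollment cover background data, consent, randomisation and an office visit; none mentions QOL. The Office Visit row is marked at enrolment and at 3, 6, 12, 18 and 24 months. The footnote lets research visits be completed in several ways, including from a registry. Enrollment and Informed Consent has the coordinator time research visits to match clinical LVAD visits, but its list of data to be collected does not include QOL.

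On timing, Study Population states: "Consent and randomization will occur either at the time of index hospitalization discharge or during the first post-discharge LVAD/ICD clinic visit". Randomization adds: "Neither the patient nor treatment team are blinded to the randomization or programming assignment". ICD Programming states: "The ICD re-programming will be performed during the routine pre-discharge ICD check during the LVAD implant hospitalization or at routine LVAD clinic follow-up", the latter within 30 days.

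On analysis, the Statistical Plan says: "For continuous outcomes, linear regression will be utilized". Covariates may be brought in later if needed. Baseline QOL is not named as one.

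**The concern.** The hypothesis claims an improvement in QOL, yet no pre-assignment score is planned against which improvement could be measured or for which the comparison could be adjusted. A score not collected before assignment cannot be recovered later, and the option to add covariates is of no use for a variable that was never recorded.

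The 1-month score is not a substitute. By then the patient knows the assigned arm and the device may already have been reprogrammed. Adjusting for that score could remove part of the treatment effect, or carry reporting influenced by known assignment into the covariate.

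At stake are the precision of the QOL comparison and the ability to estimate change from a true baseline. The shock endpoint and the sample size are not involved.

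**Working it through.** **The plan's own figure.** The documents give no power calculation for QOL. The 280 patients are sized on shocks. Taking 2 × 17% = 34% against 34% − 15% = 19% (the plan does not state how it converts the annual rate to two years), 140 per arm gives 81.5% power, in line with the stated 80%. So 140 per arm is taken as given.

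**Inputs.** From Sample Size: 140 per arm, 80% power, two-sided 0.05. Assumed, because the documents do not give them: a continuous QOL score; correlation ρ between baseline and follow-up of 0.3, 0.5 or 0.7; for averaged scores, the same ρ between every pair of visits; complete data unless stated.

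**Formula.** In SD units, by normal approximation, the detectable difference is (1.960 + 0.842) × √(2V/n). With n = 140 and V = 1 this is 2.802 × 0.1195 = 0.335. The variance factor V is:

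- one follow-up score, unadjusted: 1
- one follow-up score, baseline-adjusted: 1 − ρ²
- one follow-up score, simple change from baseline: 2(1 − ρ)
- mean of four scores, unadjusted: (1 + 3ρ)/4
- mean of four scores, baseline-adjusted: (1 + 3ρ)/4 − ρ²

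**Results, 140 per arm (detectable difference in SD, with V in brackets).**

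| Analysis | ρ = 0.3 | ρ = 0.5 | ρ = 0.7 |
|---|---|---|---|
| One score, unadjusted | 0.335 (1) | 0.335 (1) | 0.335 (1) |
| One score, adjusted | 0.319 (0.91) | 0.290 (0.75) | 0.239 (0.51) |
| One score, simple change | 0.396 (1.4) | 0.335 (1.0) | 0.259 (0.6) |
| Four-score mean, unadjusted | 0.231 (0.475) | 0.265 (0.625) | 0.295 (0.775) |
| Four-score mean, adjusted | 0.208 (0.385) | 0.205 (0.375) | 0.179 (0.285) |

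Adjustment cuts the variance by 9%, 25% and 51% for one score. For the four-score mean the ratios 0.385/0.475, 0.375/0.625 and 0.285/0.775 give cuts of 19%, 40% and 63%. A simple change score is less precise than the unadjusted comparison at ρ = 0.3, equal to it at 0.5, and worse than adjustment at all three values.

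**Missing scores.** If 30% were missing (assumed), n = 98 per arm. The single-score figure is then 2.802 × √(2/98) = 0.400 SD unadjusted, and 0.382, 0.347 and 0.286 SD adjusted.

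**Adding month 24.** With five scores, V adjusted = (1 + 4ρ)/5 − ρ². At ρ = 0.5 this is 0.60 − 0.25 = 0.35, so the detectable difference moves only from 0.205 to 0.198 SD. The last marked QOL assessment falls 24 − 21 = 3 months before follow-up ends.

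**The case against.** **The table may not mean what it literally shows.** The Research Visit marks fall exactly in the months without an Office Visit mark. Read strictly, the same row would also mean no adverse-event assessment at 3, 6, 12, 18 or 24 months, which is unlikely to be intended when the interim looks are at 6 months and 1 year and the primary assessment is at 2 years. Research visits are also meant to coincide with clinical ones. This stands for month 24: a reader might infer that QOL is deliberately omitted there, but the documents support only an ambiguity. It is weaker for baseline, because even if QOL were taken at the enrolment office visit, nothing places it before the assignment is known. The registry may hold a pre-assignment score, but the plan neither says so nor relies on it.

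**QOL need not be short of power without a baseline.** For an assumed true difference of 0.30 SD, a single unadjusted score gives 71% power, from which a reader might infer an underpowered endpoint. That figure uses one of four scheduled scores. Under the equal-correlation assumption the unadjusted four-score mean gives 95%, 89% and 81% at ρ = 0.3, 0.5 and 0.7. This objection stands, although adjustment still improves on the four-score mean throughout.

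**The gain rests on an unknown correlation.** This also stands. Baseline would fall near LVAD discharge or the first clinic visit, so a low ρ is plausible. At 0.3 the single-score gain is small: 0.335 to 0.319 SD, or 71% to 75% power at 0.30 SD.

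**Conclusion.** The point holds as a design improvement. No section schedules a QOL score before the unblinded randomisation, and the 1-month score cannot take its place. Adjusting for a baseline score would lower the detectable difference by 0.016 to 0.096 SD for one follow-up score (0.335 − 0.319; 0.335 − 0.239), and by 0.023 to 0.116 SD for the four-score mean (0.231 − 0.208; 0.295 − 0.179), over assumed ρ of 0.3 to 0.7 with 140 per arm and complete data. The four-score figures also assume equal correlation between visits. The instrument is not named, so a continuous score is itself an assumption.

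A reader might infer that the QOL comparison is invalid without a baseline. The documents do not support that: randomisation makes the unadjusted comparison of follow-up scores valid, and the Statistical Plan promises no baseline-adjusted or change analysis that would fail. Nor does adjustment cure everything. It does not remove reporting bias from the open-label design, and it does not replace scores lost to death, transplant or drop-out.

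The 24-month question is secondary. No section ties QOL to month 24, and a score there adds little precision; its value is alignment with the 2-year follow-up.

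**What to change.** Mark the QOL questionnaire at Screening/Enrollment in the Follow Up table, and state that the patient completes it after consent and before the assignment is revealed. In the Statistical Plan, name baseline QOL in advance as a covariate in the linear regression already planned, or in a mixed model over the follow-up visits, and do not rely on a simple change score.

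As a clarification, state in the table whether QOL is also collected at office visits, and mark it at the existing 24-month visit.

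The cost is one questionnaire at each of two visits already in the schedule: a little patient and coordinator time, with no new visits and no change in sample size. The baseline item has to be in place before a patient is randomised, since it cannot be collected afterwards.

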## **Enrollment and Informed Consent**

The multi-disciplinary study investigators include physicians and nurse practitioners in electrophysiology, HF, and cardiothoracic surgery. The LVAD nurse practitioners, HF physicians, and surgical team will identify eligible patients and hold a preliminary discussion with patients about the study. A research coordinator will then verify eligibility, obtain informed consent, complete randomization, direct the device clinic on assigned programming changes (if any), and coordinate research follow-up visits to coincide with clinical LVAD visits for data collection on ICD therapies, symptomatology, HF hospitalizations, and death/transplantation.

All subjects who complete the informed consent process, sign and date the informed consent form are considered enrolled in the Stop Shock LVAD study. Subjects enrolled in this investigation must be followed per protocol.

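### The only scheduled adverse event assessment can be completed without contacting the patient, and the office visits carry no adverse event item, so syncope without medical contact can be missed

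*Combined protocol and SAP*

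**What the plan says.** The schedule table in the Follow Up section has one row for adverse events: "Research Visit *, including assessment for AE/SAE/QOL". It is marked at months 1, 9, 15 and 21. The footnote to that row reads: "Can be completed in-office, by phone, medical record review and from the Interagency Registry of Mechanically Assisted Circulatory Support/NIH registry". It sets no minimum of patient contact. The Office Visit row is marked at enrollment and at months 3, 6, 12, 18 and 24; it has no asterisk and no adverse event item. Syncope is not named in the table and is not defined as an outcome anywhere.

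Other sections bear on the point:

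- Enrollment and Informed Consent says the coordinator will "coordinate research follow-up visits to coincide with clinical LVAD visits for data collection on ICD therapies, symptomatology, HF hospitalizations, and death/transplantation".
- The synopsis table describes follow-up as "Routine post-LVAD care; no additional study visits" and lists under primary endpoints "Any ICD shock Mortality Syncope". The Introduction names ICD shock as the primary endpoint and puts syncope among the data to be collected. The hypothesis there and in Objectives and Endpoints includes no increase in syncope; no margin is given.
- Randomization states: "Neither the patient nor treatment team are blinded to the randomization or programming assignment".
- ICD Programming states: "In the physician-discretion arm, ICD shocks delivered for VA routinely result in emergency department visits and hospitalizations". For sustained arrhythmia in the ultra-conservative arm it says "a symptom-driven care pathway will be implemented involving same-day cardioversion with the associated routine care".

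**The concern.** A faint that leads to no call, clinic contact or admission leaves nothing in a chart or a registry. Device interrogation may show an arrhythmia, but not whether the patient lost consciousness. Asking the patient or caregiver is the dependable source, and the plan never requires it at a visit that carries adverse event assessment.

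The stake is the safety half of the hypothesis. When the hoped-for result is no increase, each missed event shrinks the absolute difference and makes that result easier to reach, even if events are missed equally in both arms. If capture also differs between arms, the comparison itself is biased. That is possible here: staff know the assignment, and a shock in the physician-discretion arm tends to produce an emergency visit at which a faint would be written down.

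**Working it through.** **What is scheduled, side by side**

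| Item | Months marked | Adverse event item | Patient contact required |
|---|---|---|---|
| Research visit | 1, 9, 15, 21 | Yes | No (footnote) |
| Office visit | 3, 6, 12, 18, 24 | No | Yes, by its nature |
| Device interrogation | All nine | No | No (may be remote) |

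No post-enrollment month carries both the adverse event item and an office visit. The last scheduled adverse event assessment is at month 21 of 24.

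**The plan's own figure.** The only calculated figure is 280 patients for ICD shock. Compounding 17% per year gives a two-year risk of 1 − 0.83² = 31.1%. With a 15-point reduction, 31.1% v 16.1% at two-sided 0.05, 80% power and continuity correction needs 138 per arm, 276 in all, close to 280. This point leaves that number unchanged. There is no figure for syncope to reproduce.

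**Illustration, all rates assumed.** Let the true two-year syncope risk be p in each arm and capture be s, so the observed risk is s × p. With n = 140 per arm, two-sided 0.05 and normal approximation,

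power = Φ{[(p₂ − p₁) − 1.96 √(2p̄(1 − p̄)/n)] / √([p₁(1 − p₁) + p₂(1 − p₂)]/n)}.

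Full capture, 10% v 20%: p̄ = 0.15; 1.96 × 0.0427 = 0.0837; (0.10 − 0.0837)/0.0423 ≈ 0.39; power 65%.

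Capture of 70% in both arms: observed 7% v 14%; p̄ = 0.105; 1.96 × 0.0366 = 0.0718; (0.07 − 0.0718)/0.0364 ≈ −0.05; power 48%.

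Power when the true risk is doubled in the ultra-conservative arm (capture is given as physician-discretion/ultra-conservative):

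| True risks | Full | 70/70 | 90/70 | 90/50 |
|---|---|---|---|---|
| 5% v 10% | 35% | 26% | 14% | 4% |
| 10% v 20% | 65% | 48% | 26% | 5% |
| 20% v 40% | 96% | 82% | 51% | 6% |
| Observed risk ratio | 2.0 | 2.0 | 1.56 | 1.11 |

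If the true risks are equal, 90/70 capture gives an observed ratio of 0.70/0.90 = 0.78, and 90/50 gives 0.50/0.90 = 0.56. The reverse pattern, 70/90, gives 0.90/0.70 = 1.29, a false excess. Equal incomplete capture costs power but leaves the ratio unchanged; bias in the ratio needs capture to differ by arm.

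**The case against.** A reader might infer that the protocol itself says medical contact is more likely in the physician-discretion arm, so that syncope is under-counted in the other. The documents do not support this. ICD Programming describes contact after shocks, not after syncope, and makes no comparison between arms. The sentence just before it gives the ultra-conservative arm a symptom-triggered route to same-day care, which would also be documented. That arm has a uniform monitor zone at 150 bpm, and both arms are interrogated at all nine time points, so an episode there may leave a device record that prompts questions. Unblinded staff might ask about symptoms more closely in that arm. The unequal-capture figures are also demanding. If capture is 50% without a shock and 100% with one, capture is 0.5 + 0.5x, where x is the share of syncope accompanied by a shock; 90/50 then needs x = 0.8 in one arm and 0 in the other.

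A reader might also infer that follow-up rests on records alone. It does not: there are five post-enrollment office visits, and Enrollment and Informed Consent has symptoms collected at research visits timed with clinic visits. The footnote joins its modes with an and, so they may be meant in combination, and a quality-of-life questionnaire would ordinarily need the patient. Study Rationale also cites a case series in which syncope from ventricular arrhythmia was rare.

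Most of this stands, and it limits the claim. It does not close the gap. The office visits offer an opportunity without an item, a question set or a definition, and the footnote is permissive whichever way it is read.

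**Conclusion.** The point holds in limited form. Followed as written, the plan allows every scheduled adverse event assessment to be completed without speaking to the patient, and it assigns no such assessment to the visits where the patient is seen. Unattended syncope can be missed. This matters because the synopsis makes syncope a primary endpoint, though the Introduction gives it lower standing, and because the aim is to show no increase.

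The size is unknown. On assumed risks of 10% v 20%, the loss of power at equal 70% capture is 17 points (65% to 48%); across the assumed risks shown it runs from 9 points (35% to 26%) to 17. These figures treat the capture rate as applying to all syncope over two years, whereas the footnote covers four of nine time points, so the real loss may be smaller. Unequal capture between arms is a reasonable possibility, not a finding; neither its direction nor its size is established. The planned 280 is unaffected. This is an inexpensive improvement to ascertainment.

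**What to change.** Reword the footnote and add an adverse event and syncope item to the Office Visit row, so that at every post-enrollment time point (months 1, 3, 6, 9, 12, 15, 18, 21 and 24):

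- syncope and adverse events are assessed by direct contact with the patient or caregiver, in office or by phone;
- the same fixed syncope questions and the same written outcome definition are used in both arms;
- record review and the registry supplement or confirm that contact, and replace it only when the patient has died or cannot be reached;
- the mode used is recorded for each assessment, so that it can be compared between arms.

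The cost is footnote wording, a short question set, a definition and modest time for the existing coordinator. Phone is already a permitted mode, so the four research time points need at most a call. The five office visits already bring the patient in and need only the questions. No study visit is added.
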